7.7 Handling of missing data and data outside range

No imputation of missing data for variables used in the primary or secondary analyses will be performed. Only observed data will be used in the analyses.

If the date on a 3-month or 12-month form is either missing or unreadable we assume that the form was filled out at exactly 3 months or 12 months, respectively. For the PP analysis of the primary endpoint, the 3-month observation of self-reported oxygen utilization will be used if the 12-month observation is missing.

Data from forms submitted after hospitalization will not be used in the analysis of the primary outcome.

7.8 Evaluation of safety

Adverse events will be presented as plain text in a listing. If applicable, the number of adverse events will be compiled per treatment group in a frequency table. No statistical test between the treatment groups will be performed.

8 Analysis data base definitions

8.1 Data sources and terminology

Swedevox include individual participant data including the date and main reason of starting LTOT; arterial blood gases (PaO₂ and PaCO₂) on air and on oxygen; in some cases the oxygen saturation (SaO₂); equipment, prescribed oxygen flow rate (liters/min); prescribed treatment duration (h/day); age; gender; height and weight (for calculation of the body mass index); performance status; and spirometry that should be representative of the patient's stable status before starting LTOT: the forced expired volume in one second (FEV1) and forced vital capacity (FVC). These data will be used for characterizing the participants at study start and for categorization into analysis groups according to severity of hypoxemia and underlying cause of starting LTOT (COPD vs. ILD).

More detailed information regarding data sources will be described in DMP (Data Management Plan)

9 Determination of sample size

9.1 Limit of non-superiority and Hypotheses

A time-to-composite event survival analysis, with composite event equal to death or 1st hospitalization as endpoint, is used. The hypothesis of non-superiority of continuous oxygen is tested. The null hypothesis is rejected if the hazard ratio (HR) of continuous oxygen vs. 15h/day exceeds the limit 0.67. The use of oxygen is burdensome and with hospitalization, being less serious than death, incorporated into the primary endpoint, the HR of 0.67 was judged to be the appropriate limit for the composite primary outcome. This was the difference in mortality or hospitalization that the investigators judged to be clinically worthwhile. (See also section 10 Changes to the planned analysis.)

$H_0: HR_{24h/day} \leq 0.67$

$H_A: HR_{24h/day} > 0.67$ Continuous oxygen is not better than 15h/day;

If significance is obtained, the conclusion is that LTOT prescribed for 24 h/day does not reduce the rate of the composite event of all-cause death or 1st hospitalization at 1 year compared to LTOT prescribed for 15 h/day in patients starting LTOT for chronic respiratory failure.

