7.5 Analysis of primary variable

The primary endpoint of the composite event of death or 1st hospitalization at 1 year (day 365; day 0 being the day of randomization) is analyzed with Cox's proportional hazards model. Proportional hazard assumption will be investigated using graphical diagnostics based on the Schoenfeld residuals. The results will be presented as the hazard ratio (HR) for LTOT 24h/day vs. 15h/day with 90% two-sided

confidence interval and the one-sided p-value for the hypothesis test if the lower limit exceeds 0.67 (see section 9.1) A two-sided p-value for the difference between treatments will also be presented. (OS table 10 and table 11). The ITT population will be used for primary analysis but all endpoints will be analyzed according to both the ITT and the Per Protocol (PP) principle.

Statistical significance is defined as a p-value < 0.05. As a sensitivity analysis, the primary analysis is repeated adjusting for sex and age at randomization in years. A frailty model will be performed with “center” as a random effect to account for the clustering by hospital.

Cases withdrawing from LTOT treatment are for the primary analysis handled as

- 1) Per protocol, if it is due to improved oxygenation.
- 2) Having reached endpoint, if it is due to adverse event (such as excessive nose bleeding etc.).
- 3) Censored, if it is due to cancellation of treatment for reasons other than treatment allocation or adverse events (such as starting to smoke etc.).

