9.2 Sample size calculation

Calculation of the final required sample was based on a time-to-composite event survival model with the use of the Cox proportional hazards (PH) model and checked against the results of the log-rank test statistic. Assuming 80% power to verify a hazard ratio for death or 1st hospitalization of more than 0.67 in the 24h group vs. the 15h group, a one-sided type I error rate of 0.05, and an event rate of 80% based on Swedevox registry data, we calculated a total sample size of 189 patients with Cox PH and 181 using the log-rank statistic. Making allowances for a loss of patients in the PP analysis, the final planned total trial size is 230, with 1:1 allocation. No patient is expected to be lost to follow-up for the primary composite endpoint of death or 1st hospitalization in the ITT population, due to the use of national registries. The following R code for a Cox PH non-inferiority calculation, inverting the hypothesized hazard ratio from the non-superiority hypothesis for this study, was used for the sample size calculation:

#Hazard Ratio, hr

#Null-Hypothesis Hazard Ratio, hr0

#Overall Probability of Event, pE

#Proportion of Sample in Group 'A', pA

```
> hr=1
```

```
> hr0=1.5
```

```
> pE=0.8
```

```
> pA=0.5
```

```
> alpha=0.05 # 1-sided test
```

```
> beta=0.20
```

```
> (n=((qnorm(1-alpha)+qnorm(1-beta))/(log(hr)-log(hr0)))^2/(pA*(1-pA)*pE))
```

```
[1] 188.0317
```

```
> ceiling(n)
```

```
[1] 189
```

10 Changes to the planned analysis (2020-01-22)

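### SAP 9.1 fixes the conclusion of a significant test as no reduction, but rejecting HR ≤ 0.67 excludes only reductions of 33% or more

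*SAP*

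**What the plan says.** Section 9.1 of the SAP sets the primary hypotheses as H0: HR ≤ 0.67 against HA: HR > 0.67 for 24 h/day versus 15 h/day. It introduces the test with "The hypothesis of non-superiority of continuous oxygen is tested" and explains the limit of 0.67 with "This was the difference in mortality or hospitalization that the investigators judged to be clinically worthwhile".

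Two statements in the same section then leave the limit out. HA is labelled "Continuous oxygen is not better than 15h/day". The consequence of a significant test is fixed as: "If significance is obtained, the conclusion is that LTOT prescribed for 24 h/day does not reduce the rate of the composite event".

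Section 7.5 carries out the test through the lower limit of a two-sided 90% confidence interval and reports the "one-sided p-value for the hypothesis test if the lower limit exceeds 0.67". It adds: "A two-sided p-value for the difference between treatments will also be presented". Table 10.1 of the output shells has a column for each of these p-values. Neither place ties the comparison with HR = 1 to the conclusion in 9.1.

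**The concern.** Rejecting H0: HR ≤ 0.67 establishes HR > 0.67. That region includes HR 0.70, 0.80 and 0.90, all of which are reductions in the rate of death or first hospitalization. The test therefore supports the statement that 24 h/day does not lower the hazard by 33% or more. It does not support the statement that 24 h/day does not lower it.

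The fixed sentence is the one that a report or abstract would take over. Followed as written, it would turn a result that is inconclusive about a modest benefit into a finding of no benefit, on an endpoint that includes death.

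**Working it through.** **Inputs**

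- Limit 0.67: section 9.1.
- Two-sided 90% CI, lower limit compared with 0.67: section 7.5.
- "a one-sided type I error rate of 0.05, and an event rate of 80% based on Swedevox registry data": section 9.2.
- "the final planned total trial size is 230, with 1:1 allocation": section 9.2.
- Approximation: ln HR is normal with SE = 2/√(events), for 1:1 allocation and proportional hazards.

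**The plan's own figure**

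Section 9.2 inverts the limit to 1.5 and assumes a true HR of 1 with 80% power:

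n = [(1.645 + 0.842) / (ln 1 − ln 1.5)]² / (0.5 × 0.5 × 0.8) = 188.03, rounded up to 189.

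This reproduces the SAP. The sample size is not in question.

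**Where significance starts**

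- Events: 230 × 0.80 = 184. SE = 2/√184 = 0.1474.
- Half-width of the 90% CI on the log scale: 1.645 × 0.1474 = 0.2425.
- Smallest observed HR whose lower limit reaches 0.67: 0.67 × exp(0.2425) = 0.854.
- Upper 90% limit at that point: 0.854 × exp(0.2425) = 1.09.

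An observed reduction of about 15%, with a 90% CI of 0.67 to 1.09, would thus lead to the sentence that there is no reduction.

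**How often the sentence would be used**

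P(significant) = Φ[(ln HR − ln 0.67)/SE − 1.645]

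| True HR | (ln HR − ln 0.67)/SE | P(significant) |
|---|---|---|
| 0.80 | 1.203 | 33% |
| 0.90 | 2.002 | 64% |
| 1.00 | 2.716 | 86% |

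At 0.80 and 0.90, rejecting H0 is correct, because the true HR does exceed 0.67. These are not error rates of the test. They show how often the fixed sentence would be written when a true reduction exists.

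**What a result does exclude**

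At an observed HR of 1.00 the 90% CI is exp(±0.2425) = 0.785 to 1.27. Reductions above 21.5% are excluded and smaller ones are not. The reach of the conclusion depends on the observed lower limit, so no fixed sentence without a limit can be right for every significant result.

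**Can the sentence clash with a significant benefit?**

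- A 90% CI wholly below 1 needs an observed HR under exp(−0.2425) = 0.785.
- A two-sided p < 0.05 against HR = 1 needs an observed HR under exp(−1.96 × 0.1474) = 0.749.
- Both lie below the 0.854 at which significance starts, so neither can occur together with it. The overlap would open only at about 270 events (90% CI) or 324 events (two-sided p < 0.05).

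**Range**

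| Events | SE | Observed HR at which significance starts | P(significant) at true HR 0.90 |
|---|---|---|---|
| 151 (189 × 0.80) | 0.1628 | 0.876 | 57% |
| 161 (230 × 0.70, assumed rate) | 0.1576 | 0.868 | 59% |
| 184 (230 × 0.80) | 0.1474 | 0.854 | 64% |
| 207 (230 × 0.90, assumed rate) | 0.1390 | 0.842 | 68% |

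**The case against.** The strongest reply is that the limit stands all around the sentence. The heading of 9.1 names it, the text calls the test one of non-superiority, 0.67 is described as the clinically worthwhile difference, and H0 and HA are printed just above. In that setting the disputed wording can be read as plain language for no worthwhile reduction. The reporting also works against a misreading: section 7.5 and Table 10.1 give the HR, the 90% CI and a p-value for HR = 1, and Figure 5 of the output shells plots the interval against the non-superiority limit. Nothing in the test, the populations or the decision threshold is wrong. It is also no criticism of this plan in particular that a significant result rarely has a lower limit of 1 or more, since non-superiority designs are not built to achieve that.

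Most of this stands, and it lowers the weight of the point. A careful reader of the full section can recover the right meaning, and a reader of the results can see which reductions remain possible. It does not remove the point. The sentence and the label of HA are the two places where the SAP says what a significant result means, and both omit the limit. None of the reporting items is linked to the conclusion or narrows it.

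A further fair remark is that the primary objective in 4.1.1 asks its question without a limit too, so a change confined to 9.1 would leave the two out of step.

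**Conclusion.** The point holds. The conclusion rule in 9.1 is wrong as written: a significant test excludes a hazard reduction of 33% or more, not every reduction. At the planned size the sentence would apply from an observed HR of 0.854 upwards, and it would be used with probability 33% at a true HR of 0.80 and 64% at 0.90. These figures rest on the SAP's 80% event rate, all 230 patients analysed, proportional hazards and the normal approximation. Across 151 to 207 events the threshold stays between 0.876 and 0.842.

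The flaw is one of interpretation and should be corrected, but it does not affect the validity of the analysis. Its harm is confined to presenting an inconclusive modest effect as no effect. It cannot lead, at the planned number of events, to denying a benefit that the 90% CI or the two-sided p-value would show as significant.

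**What to change.** Replace the conclusion in section 9.1 with a statement tied to the limit, for example: *If the test is significant, a reduction of 33% or more in the hazard of death or first hospitalization with 24 h/day (HR ≤ 0.67) is excluded; whether smaller reductions are also excluded is read from the lower limit of the observed 90% CI.* Relabel HA as *not better by the specified limit*. For consistency, add to section 4.1.1 that the question is answered with respect to this limit.

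The cost is a change of SAP wording and a slightly weaker headline claim. The test, alpha, sample size, populations and output shells are unchanged.

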9.2 Sample size calculation

Calculation of the final required sample was based on a time-to-composite event survival model with the use of the Cox proportional hazards (PH) model and checked against the results of the log-rank test statistic. Assuming 80% power to verify a hazard ratio for death or 1st hospitalization of more than 0.67 in the 24h group vs. the 15h group, a one-sided type I error rate of 0.05, and an event rate of 80% based on Swedevox registry data, we calculated a total sample size of 189 patients with Cox PH and 181 using the log-rank statistic. Making allowances for a loss of patients in the PP analysis, the final planned total trial size is 230, with 1:1 allocation. No patient is expected to be lost to follow-up for the primary composite endpoint of death or 1st hospitalization in the ITT population, due to the use of national registries. The following R code for a Cox PH non-inferiority calculation, inverting the hypothesized hazard ratio from the non-superiority hypothesis for this study, was used for the sample size calculation:

#Hazard Ratio, hr

#Null-Hypothesis Hazard Ratio, hr0

#Overall Probability of Event, pE

#Proportion of Sample in Group 'A', pA

```
> hr=1
```

```
> hr0=1.5
```

```
> pE=0.8
```

```
> pA=0.5
```

```
> alpha=0.05 # 1-sided test
```

```
> beta=0.20
```

```
> (n=((qnorm(1-alpha)+qnorm(1-beta))/(log(hr)-log(hr0)))^2/(pA*(1-pA)*pE))
```

```
[1] 188.0317
```

```
> ceiling(n)
```

```
[1] 189
```

10 Changes to the planned analysis (2020-01-22)

The original design of this trial was based on a time-to-event survival analysis with death as endpoint and the hypothesis of non-superiority of continuous oxygen with a hazard ratio (HR) of 0.83 (larger than this would indicate non-superiority). This was the difference in mortality that the investigators judged to be clinically worthwhile. With the current design, which was specified in amendment 3 (2020-01-22), time-to-composite event survival analysis is used, with composite event equal to death or 1st hospitalization. Since the use of oxygen is burdensome and hospitalization less serious than death, an HR of 0.67 was judged to be appropriate for the composite primary outcome. The recently published large study of LTOT (LOTT) (see protocol reference 13) had an HR of 0.60 in their amendment for the composite endpoint of death or 1st hospitalization and an expansion of the primary analysis population, but that study is for supplemental oxygen vs. none (which should reduce the HR) and patients that were less ill with milder hypoxemia (which should increase the HR) and thus not directly comparable.

Summary of differences as compared to the original protocol

1. A composite event of death or 1st hospitalization, instead of death as the event.
2. A lower limit of non-superiority; 0.67 instead of 0.83.
3. The primary analysis is based on all randomized patients, instead of only the COPD patients.
4. A simplification of the secondary analyses due to the reduction of the sample size.

11 Description of derived variables

The description of derived variables is attached in appendix Draft_SAP_v1.0 (DV).docx.

12 Description of output

The output specification (output shells, OS), describing tables, graphs and lists that will be included in the study report, is attached in appendix Draft_SAP_v1.0 (OS).docx.

13 Statistical software

Statistical analyses will primarily be performed using SAS v. 9.4 or later and/or R (Version 4.2.3).

14 References

- [3] Fine, J. P., and Gray, R. J. (1999). "A Proportional Hazards Model for the Subdistribution of a Competing Risk." *Journal of the American Statistical Association* 94:496–509.

DERIVED VARIABLES

*Socialstyrelsen will provide us with the date of event. Time to event (in days) will be calculated by UCR

*Time to composite event (All-cause mortality/ All-cause Hospitalization)	Included in the order from Socialstyrelsen
*Time to all-cause mortality	Included in the order from Socialstyrelsen
*Time to 1st hospitalization	Included in the order from Socialstyrelsen
Mortality from respiratory disease	respiratory disease or infection (A40; J00-J99)
Mortality from cardiovascular disease	Underlying cause of death (UCD) heart disease (I00-I99)
Hospitalization from respiratory disease	UCD respiratory disease or infection (A40; J00-J99)
Hospitalization from cardiovascular disease	UCD heart disease (I00-I99)
Time to Mortality from respiratory disease	Death (from respiratory disease) date – Study start date
Time to Mortality from cardiovascular disease	Death (from cardiovascular disease) date – Study start date
Time to Hospitalization from respiratory disease	Date of hospitalization from respiratory disease – Study start date
Time to Hospitalization from cardiovascular disease	Date of hospitalization from cardiovascular disease – Study start date
Time from start until the patient stops being treated	End of treatment – Date for start of treatment
Discontinued LTOT	From Swedevox Registry
Withdrawals	DATE_OF_LTOT_WITHDRAWAL REASON_W
ITT	All randomized patients that start LTOT
PP	A randomized patient will be excluded from the PP set if LTOT has been discontinued before the primary outcome assessment or the mean LTOT utilization during follow-up to the primary endpoint is below 20 h/day for the 24 h/day group, and below 13 h/day or above 17 h/day in the LTOT 15 h/day group
COPD	J44; exacerbation: J44.0 and J44.1
Heart disease	I00-I99
Respiratory disease or infection	A40; J00-J99
fev1/fvc	FEV1/FVC
BMI	WEIGHT(kg)/(HEIGHT (m)*HEIGHT (m))
Age	Round down (RANDOMIZATION_DATE - DATE_OF_BIRTH)/365.25
Duration of treatment	Number of days with treatment during the study
Self-rated hours of oxygen	Self-reported oxygen use (mean hours/24h) is categorized using 1) average use since starting LTOT, or (if missing) mean h/day last week; using the

	questionnaire at 12 months, or (if missing) 3 months (and the described algorithm used for each time point).
Subgroup 1 Participants with more severe resting hypoxemia at LTOT start	PaO ₂ < 7.4 kPa breathing air
Subgroup 2 Participants with more moderate hypoxemia at LTOT start	PaO ₂ 7.4–8.0 kPa breathing air
Subgroup 3 Participants with spirometry verified COPD	Primary diagnosis COPD or emphysema, and FEV ₁ /FVC < 0.7 after bronchodilation) [defined using primary diagnosis + spirometry data in Swedevox]
Subgroup 4 Participants with other conditions than COPD	Other primary diagnosis than COPD in Swedevox

OUTPUT SHELLS

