4.2.2 Secondary outcome variables

- Mortality rate from all causes at 3 and 12 months
- Mortality rate from respiratory disease at 3 and 12 months
- Mortality rate from cardiovascular disease at 3 and 12 months
- Hospitalization rate from all causes at 3 and 12 months
- Hospitalization rate with a primary diagnosis of respiratory disease or respiratory infection at 3 and 12 months
- Hospitalization rate with a primary diagnosis of cardiovascular disease at 3 and 12 months
- Rate of an incident diagnosis of cardiovascular disease at 3 and 12 months

Self-reported questionnaire data collected at 3 and 12 months:

- Self-rated oxygen utilization
- Breathlessness (Multidimensional Dyspnea Profile; MDP)
- Fatigue (FACIT-Fatigue)
- Informant-rated cognition (IQCODE and FAQ)
- Self-rated cognition (BAS)
- Health-related quality of life (CAT and EQ5D-5L)
- Global impression of change from baseline (GIC)
- Self-reported physical activity
- Preference of continuing treatment

5 Study design

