5.4.2 Registry-based follow-up

All 48 units prescribing and managing LTOT in Sweden report to the National Registry for Respiratory Failure (Swedevox). Data on patient characteristics and the prescribed oxygen therapy are obtained from Swedevox. The completeness of the baseline data will be checked using Swedevox and optimized through contacts with participating centers by the national Swedevox coordinator and by the Study Coordinator.

The main endpoints of mortality and hospitalizations are assessed using national Swedish governmental registries: date and causes of death (Causes of Death Register), and the date and diagnoses/procedural codes of hospitalizations (National Patient Register of in- and outpatient care). Data are cross-linked

between registers using each participant's unique Swedish identity number. In addition, data will be obtained on dispensed outpatient medications (Prescribed Drug Register). Endpoints are assessed at 3 and 12 months after randomization (study end).

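### The derived-variable table defines respiratory and cardiovascular hospitalization by underlying cause of death instead of the primary diagnosis of the admission

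*SAP*

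**What the plan says.** The derived-variable table appended to the SAP has four cause-specific rows. Respiratory mortality is given by ICD codes A40 and J00-J99 with no further qualifier. Cardiovascular mortality is given as "Underlying cause of death (UCD) heart disease (I00-I99"), which is the only place where UCD is spelled out; the abbreviation list in Section 3 does not contain it. Hospitalization from respiratory disease is then given as "UCD respiratory disease or infection (A40; J00-J99"), and hospitalization from cardiovascular disease as UCD heart disease with codes I00-I99.

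Section 4.2.2 names the same two outcomes differently: "Hospitalization rate with a primary diagnosis of respiratory disease or respiratory infection at 3 and 12 months" and "Hospitalization rate with a primary diagnosis of cardiovascular disease at 3 and 12 months". Section 5.4.2 draws causes of death from the Causes of Death Register and, separately, the dates and "diagnoses/procedural codes of hospitalizations (National Patient Register of in- and outpatient care"). Section 7.6 analyzes hospitalizations by Fine-Gray regression with death as the competing event.

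Two lesser points sit beside this. The matching time rows count from study start, for example "Date of hospitalization from respiratory disease – Study start date", while Section 7.5 sets day 0 at randomization and the Table 5 shell counts from randomization. Figure 4 in the output shells asks for Kaplan-Meier curves for all primary and secondary outcomes.

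**The concern.** An underlying cause of death is a property of a death, not of an admission. A patient alive at the end of follow-up has none. Under the table's rule, a survivor admitted with pneumonia is not a respiratory case, while a patient admitted for a hip fracture who later dies of COPD is one. Whether an admission counts would depend on a death that comes later, so a mortality difference between the arms would carry over into the hospitalization hazard ratio. It would also undercut the Fine-Gray analysis, in which death competes with the event and is not a condition for it.

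The derived-variable table is what a programmer implements. Neither outcome is among those that the SAP's opening section leaves to the sponsor. Both appear in the shells: hazard ratios in Tables 5.13–5.24 and 11.1–11.6 and counts in Table 9, at 3 and 12 months, for ITT, PP and four subgroups.

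**Working it through.** **Text comparison**

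| Source in SAP | Respiratory hospitalization | Cardiovascular hospitalization |
|---|---|---|
| Section 4.2.2 | primary diagnosis of the hospitalization | primary diagnosis of the hospitalization |
| Section 5.4.2 | admission diagnoses, National Patient Register | same |
| Section 7.6 | death is a competing event | same |
| Derived-variable table | UCD, A40; J00-J99 | UCD, I00-I99 |

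The first three rows agree with each other; the fourth does not fit them. The code ranges are not in dispute.

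A displaced table cell cannot explain the mismatch. UCD appears in three of the four cause-specific rows, but only two of those rows concern mortality. However the cells are shifted, at least one hospitalization row carries UCD.

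**Size**

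The SAP gives no figure for these two outcomes, so there is none to reproduce. Section 9.2 gives 230 planned patients and "an event rate of 80% based on Swedevox registry data".

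- Patients with a composite event: 0.80 × 230 = 184. Each either died within the year or was hospitalized and survived it, so hospitalized survivors = 184 − deaths.
- One-year mortality is not stated. Assumed range: 20–40%.

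| Assumed mortality | Deaths | Hospitalized survivors | Share of 184 |
|---|---|---|---|
| 20% | 46 | 138 | 75% |
| 30% | 69 | 115 | 62.5% |
| 40% | 92 | 92 | 50% |

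None of the hospitalized survivors could be a case under the UCD rule. If 25–75% of them had the relevant primary diagnosis (a second assumption), the missed cases for that outcome run from 0.25 × 92 = 23 to 0.75 × 138 = 103.5, or about 104. Misclassified admissions among patients who died come on top and are not counted here.

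**Figure 4 (minor)**

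This check concerns all-cause hospitalization. Assume that deaths are censored in the Kaplan-Meier curve, that hazards are constant, and that 80% have an event by one year. With h the admission hazard and d the hazard of death before admission, h + d = −ln(0.2) = 1.609. The Kaplan-Meier value at one year is 1 − exp(−h); the cumulative incidence is (h/1.609) × 0.8.

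| d per year (assumed) | Kaplan-Meier | Cumulative incidence | Difference, points |
|---|---|---|---|
| 0.2 | 75.6% | 70.1% | 5.5 |
| 0.3 | 73.0% | 65.1% | 7.9 |
| 0.4 | 70.2% | 60.1% | 10.0 |

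Only the height of the curves is affected; no hazard ratio or test changes.

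**The case against.** The strongest reply is that this is a drafting slip which the SAP itself resolves. Sections 4.2.2, 5.4.2 and 7.6 and the table's own time rows, which use the date of hospitalization, all point to the admission diagnosis. A statistician would probably notice the oddity when programming, and Section 8.1 leaves further detail on data sources to a data management plan that is not at hand. It is fair to conclude that the intention is clear. But the operative definition still says something else, and a SAP exists to settle definitions before unblinding.

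The case counts rest largely on assumptions. Mortality and the cause shares are not in the SAP, and the result spans more than a fourfold range. The 50–75% has all composite events as its denominator, so it is not the share of true respiratory or cardiovascular cases lost. This stands: the figures show the order of magnitude, and the contradiction does not need them.

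The start-date point is loose terminology more than a demonstrated conflict, since the SAP elsewhere uses study start and study end at participant level. Figure 4 is descriptive, and its shell does not say that deaths are censored. Both are tidying points and add no weight.

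Two objections to a bare replacement of UCD also stand and are met in the fix: the respiratory mortality row has no UCD to keep, and first admission can be read in two ways.

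**Conclusion.** The concern holds. The two hospitalization rows of the derived-variable table contradict Sections 4.2.2, 5.4.2 and 7.6 and are wrong as written. Programmed literally, they would exclude every hospitalized survivor: 92 to 138 of the 184 patients expected to have a composite event, if one-year mortality is 20–40%. Between about 23 and 104 true cases of an outcome would be missed if 25–75% of those survivors had the relevant primary diagnosis. Mortality and cause share are both assumptions.

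The damage is confined to two secondary outcomes at 3 and 12 months. The rows should be corrected before programming, but the trial's main conclusion does not depend on them.

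**What to change.** In the derived-variable table:

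- **Respiratory hospitalization:** first inpatient admission after randomization in the National Patient Register with a primary diagnosis in A40 or J00-J99.
- **Cardiovascular hospitalization:** the same, with a primary diagnosis in I00-I99.
- **Meaning of first:** state that this is the first admission with a qualifying diagnosis, whether or not admissions for other causes came before it. This fits Section 7.6, which names only death as the competing event.
- **Mortality rows:** keep UCD here only, and write it into the respiratory mortality row, which now lacks it.
- **Time rows:** replace the study start date by the randomization date.

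In the output shells (minor), for hospitalization outcomes in Figure 4, show cumulative incidence curves with death as the competing event.

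The cost is a few wording edits and one figure shell. The register is already named in Section 5.4.2; the one practical check is that the data delivery includes the primary diagnosis of each admission, not only the dates.
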